#### **c. Improvement of quality of life after surgery:**

The EORTCQLQ-C30 and EORTCQLQ-CR2930 scales were completed one month before and after surgery.

#### **d. Total survival and tumor-free survival:**

The total survival and tumor-free survival of patients after surgery. One year after surgery, imaging examination, endoscopy and tumor marker detection were used to

evaluate the recurrence and distant metastasis of tumors.

#### **e. Changes in gut microbiota and metabolites:**

Following diarrhea onset, significant taxonomic shifts occur in the gut microbiota, favoring the proliferation of fast-growing facultative anaerobes. *Proteus* species (primarily *Enterobacteriaceae*/*Escherichia coli*) and *Streptococcus* species (mainly *Streptococcus salivarius* and *Streptococcus gallolyticus*) show the most pronounced enrichment during early stages, with relative abundance potentially reaching 80% in fecal microbiota. The dramatic decline of obligate anaerobic gut symbionts and the oxidative changes in intestinal environment during diarrhea further promote their proliferation, as evidenced by elevated expression of genes encoding low-affinity cytochrome oxidases. This abundance increase coincides with the abrupt disappearance of obligate anaerobic gut symbionts (*Blautia*, *Prevotella*, *Faecalibacterium*, *Lachnospiraceae*, *Ruminococcaceae*, etc.), leading to depletion of related metabolites such as short-chain fatty acids. Differential analysis was conducted by detecting changes in abundance and metabolites of these associated bacterial groups.

#### **Exploratory endpoints:**

Potential organ cross-talk and molecular mechanisms of nutritional and metabolic disorders caused by RISE anastomosis. Based on the changes in patients' postoperative metabolism and stool habits, the corresponding metabolites and molecular changes in blood, stool and bile were detected to speculate the potential mechanism.

### **6. Data management and statistical analysis**

The clinical departments utilize the institution's electronic medical record system to compile relevant patient data. Clinical outcomes are systematically analyzed by designated personnel using SPSS 22.0 statistical software. Categorical data are presented as [count (%)], analyzed through  $\chi^2$ -tests. Quantitative data, validated by S-W method testing for normal distribution, are expressed as  $(\bar{x} \pm s)$  and evaluated using t-tests. Statistical significance is defined as  $P < 0.05$ .

Follow-up processing: The lost cases were included in the intention-to-treat (ITT) analysis, and multiple interpolation was used to fill in the missing data.

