treating children with congenital ileocecal valve atresia and patients requiring combined resection due to non-neoplastic causes [9], indicating potential clinical benefits of ileocecal valve reconstruction. However, these approaches also present notable limitations: (1) The relatively thin colon wall makes submucosal tunnel reconstruction prone to bowel perforation; (2) The complex procedural steps hinder clinical application and promotion.

Building on these findings, this study proposes an innovative ileocolonic anastomosis approach based on the integrated reconstruction concept of mucosal folds within the ileocecal valve and the annular muscle outside the valve. The "Revolute Insert Side-End ileocecal valve reconstruction (RISE)" method combines "revolute insertion of the ileocecal valve" with "sleeve embedding reconstruction of the colonic muscle" in the ileal pouch. Preliminary small-sample clinical data demonstrate that this RISE-based ileocecal valve reconstruction technique features simple operation and a distinct "gate effect". Compared to conventional ileocolonic side-to-side anastomosis, patients with RISE anastomosis exhibit faster postoperative intestinal function recovery and significantly improved bowel function quality, highlighting the unique advantages of RISE. Notably, there was no significant difference in short-term complications between RISE and conventional anastomosis groups, indicating good surgical safety. This study plans to conduct a multicenter clinical comparative trial combining complete laparoscopic/robot-assisted right hemicolectomy with RISE anastomosis, observing its effects on short-term and long-term complication rates, quality of life, bowel function, gut microbiota, nutrient absorption, and long-term oncological outcomes.

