## **2. Secondary purposes:**

- (1) Compare the surgical safety of the two groups (RISE anastomosis group vs. traditional anastomosis group), including intraoperative bleeding, anastomotic leakage rate (Clavien-Dindo classification), and complication rate within 30 days after surgery;
- (2) To evaluate the effects of RISE anastomosis on postoperative nutritional and metabolic disorders, including serum albumin, vitamin B12, bile acid levels, and body composition analysis (body fat percentage, muscle mass);
- (3) To analyze the improvement effect of RISE anastomosis on postoperative quality of life, and evaluate it by EORTC QLQ-C30 and QLQ-CR29 scale scores;
- (4) To explore the long-term effects of RISE anastomosis on overall survival (OS) and progression-free survival (PFS);
- (5) Detect the dynamic changes of intestinal flora abundance (such as *Proteus*, *streptococcus*, obligate anaerobic bacteria, etc.) and metabolites (such as short chain fatty acids) in the two groups after surgery to clarify the regulatory effect of RISE anastomosis on intestinal microecology.

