### **3. Sample size:**

This prospective, double-arm, single-blind, multicenter randomized controlled trial evaluated the effectiveness of RISE anastomosis with ileocecal valve reconstruction. The postoperative stool formation time served as the primary endpoint for sample size calculation. Based on our prior trial results, the stool formation rate was approximately 65% in the RISE group and 33.3% in the control group on day 2 postoperatively. With a two-tailed test level  $\alpha=0.05$  and a 1:1 group ratio, PASS11.0 software estimated minimum sample sizes of 85 cases per group. Considering a 10% dropout rate, each group required 94 additional cases ( $85 + 85 \times 10\%$ ), totaling 188 cases combined. The study employed block randomization with minimum blocks of 4 samples. Subsequently, sample allocation was determined based on regional average patient intake levels to match block sizes.

According to the number of patients with right-sided colon cancer admitted by each center per year, the number of cases was allocated proportionally among the research centers,

Table 1 Sample size allocation of each sub-center

Center units	Sample size allocation
Second Affiliated Hospital of Army Military Medical University	108
The First Affiliated Hospital of Chongqing Medical University	20
Affiliated Hospital of North Sichuan Medical College	20
Guangan People's Hospital, Sichuan Province	20
Third People's Hospital of Yibin City, Sichuan Province	20

[figure not shown]

Figure 1 PASS11.0 software interface-sample size calculation results

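### The protocol compares leakage and Clavien-Dindo complications by an unordered chi-square test at P<0.05 without a risk difference or interval, so a non-significant result could hide a large excess

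*Protocol*

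**What the plan says.** Protocol section III.6 (Data management and statistical analysis) sets a single method for categorical outcomes: "Categorical data are presented as [count (%)], analyzed through" chi-square tests. It adds a single decision rule, "Statistical significance is defined as" P<0.05. The protocol names no risk difference, confidence interval, exact test, ordered test or safety margin.

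This rule governs the first secondary objective (section II.2), which compares the surgical safety of the two arms, including "anastomotic leakage rate (Clavien-Dindo classification), and complication rate within 30 days after surgery". Sections III.4 and IV and the annex grade complications on the Clavien-Dindo scale, which is ordered from I to V with sub-grades.

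The sample size (section III.3) rests on stool formation alone. It arrives at 85 per group, then 94 per group after dropout.

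On pilot data, the research context (section I) says: "Notably, there was no significant difference in short-term complications between RISE and conventional anastomosis groups, indicating good surgical safety".

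**The concern.** RISE is a new anastomosis, so whether it leaks more than the standard one is a central safety question. Two features of the stated method fit that question poorly.

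- **Leakage may be rare.** A P-value on a few events says little about how large an excess remains possible. An estimate with an interval says it directly, and the protocol asks for none.
- **Clavien-Dindo grade is ordered.** A chi-square test on a grade-by-arm table treats the grades as interchangeable labels. It discards the information that one arm's complications are shifted upwards.

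At stake is the safety statement in the trial report. A materially higher leak rate could be written up as no significant difference, and the background section shows the investigators have already read such a result as reassuring.

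**Working it through.** **Inputs from the protocol.** Two-sided alpha 0.05; 1:1 allocation; 85 per group before and 94 after the dropout allowance (section III.3). The step to 94 reproduces: 85 x 1.10 = 93.5, rounded up to 94, and 2 x 94 = 188. The 85 itself cannot be checked, because the readable text states no power. It was in any case set for 65% v 33.3% stool formation, not for safety.

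**Inputs assumed.** The protocol gives no leak rate and no grade distribution, so a range is shown.

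**1. Power of chi-square for a tripled leak rate.** For every pair of counts (x, y), take the product of the two binomial probabilities. Sum these products over the pairs where the uncorrected Pearson statistic exceeds 3.84.

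| Leak rates | Chi-square, 94 per arm | Chi-square, 85 per arm | Fisher, 94 per arm |
|---|---|---|---|
| 1% v 3% | 13% | 11% | 3% |
| 2% v 6% | 26% | 24% | 15% |
| 3% v 9% | 40% | 36% | 30% |
| 5% v 15% | 65% | 60% | 55% |
| 8% v 24% | 87% | 83% | 82% |

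**2. What one plausible result would look like: 9/94 v 3/94 leaks.**

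- Chi-square = N(ad - bc)^2 / [n1 n2 t (N - t)], where t is the total number of leaks. Here ad - bc = 9 x 91 - 3 x 85 = 564, so 188 x 564^2 / (94 x 94 x 12 x 176) = 3.20 and P = 0.073. Fisher's exact test gives P = 0.133.
- Difference: 9.57% - 3.19% = 6.38 points.
- Wilson limits: 5.12% to 17.20% for 9/94, and 1.09% to 8.97% for 3/94.
- Newcombe lower limit: 6.38 - sqrt[(9.57 - 5.12)^2 + (8.97 - 3.19)^2] = 6.38 - 7.29 = -0.9.
- Newcombe upper limit: 6.38 + sqrt[(17.20 - 9.57)^2 + (3.19 - 1.09)^2] = 6.38 + 7.91 = +14.3.

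So a threefold observed rate is non-significant, while the same data are compatible with an excess of up to 14.3 points. Even 3 v 3 leaks leaves an excess of 6.1 points not excluded. By contrast, 12 v 4 leaks is significant (P = 0.037).

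**3. Expected counts.** With 94 per arm, the expected number of leaks per arm is below 5 when the pooled rate is under 5/94 = 5.3%. For 6 v 2 leaks it is (6 + 2)/2 = 4. For 9 v 3 it is 6, so that example does not depend on a failing approximation.

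**4. Loss from ignoring grade order.** Trials of 94 per arm were simulated under proportional odds with a common odds ratio of 2. Each simulated trial was tested by unordered chi-square and by the Wilcoxon rank-sum (Mann-Whitney) test.

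| Assumed control distribution | Chi-square | Rank test |
|---|---|---|
| 72% none, 12% I, 10% II, 6% III-V, in eight levels (4,000 trials) | 31% | 64% |
| 70 / 12 / 10 / 5 / 3% over five ordered categories (2,000 trials) | 44% | 67% |

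In the eight-level table, more than 20% of cells had expected counts below 5 in over 99% of trials. The size of the loss depends on the assumed distribution; its direction was the same in both.

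**The case against.** A reader might infer four stronger things. The documents do not support them.

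- **That the test is almost powerless, or non-significance near certain.** This depends on a leak rate the protocol does not give. Power is 13% at 1% v 3%, but 65% at 5% v 15% and 87% at 8% v 24%.
- **That a P-value is the only planned output.** Section III.6 also plans counts and percentages, from which a reader could derive the interval. Section IV adds detailed adverse-event reporting with an assessment of relation to the intervention, and the termination criteria include a qualitative rule on excess leakage.
- **That the trial will declare RISE safe if P>0.05.** No section sets such a rule. The sentence in section I describes pilot data. It shows a risk of misreading, not a decision rule.
- **That order is lost throughout.** Section II.2 speaks of rates. For a yes/no outcome order plays no part, so the ordinal point applies only where grades are compared.

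Two further objections have weight. Low power for a secondary outcome in a trial sized on its primary endpoint is not an error. And changing to Fisher's exact test would not help power: it lowers it from 40% to 30% at 3% v 9%.

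It can also be said that such detail belongs in the statistical analysis plan, which is not shown. That would answer a complaint about something left out. Here the protocol has itself fixed one test for all categorical data, and section V.7 refers to the analysis plan for centre effects.

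**Conclusion.** The point holds in a limited form. The protocol fixes one unordered, large-sample test for all categorical outcomes, gives counts and percentages but no effect estimate or interval, and applies this to rare and ordered safety outcomes. Its background section already treats non-significance as reassurance.

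At assumed base rates of 2% to 5%, power for a tripled leak rate is 26% to 65% with 94 per arm, so a true tripling could well be reported as non-significant. Where grades are compared, an unordered test gives up roughly 23 to 33 percentage points of power (67 - 44 and 64 - 31) under the assumed distributions and odds ratio of 2. All these sizes rest on assumed rates. What does not rest on them is that a non-significant P cannot show how much excess risk has been excluded, whereas an interval can. This is a fault in how the comparison is specified, not in the sample size.

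**What to change.** Amend section III.6:

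- **Leakage and 30-day complications:** report the risk difference (RISE minus control) with a 95% Newcombe or Miettinen-Nurminen interval. Base the safety statement on the upper limit, and state that P>0.05 will not be read as equal safety.
- **Clavien-Dindo grade, where it is compared:** take the worst grade per patient and use a Wilcoxon rank-sum test or an ordinal logistic model.
- **Sparse tables:** an exact test may be given where expected counts are below 5, for validity only. It lowers power, so the interval should carry the inference.

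This costs wording in the protocol and the analysis plan. It needs no extra patients, visits or data. The downside is a more cautious safety conclusion.

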## **II. RESEARCH OBJECTIVES**

### **1. Main objectives:**

To evaluate the efficacy of total laparoscopic/robot-assisted right hemicolectomy combined with ileocolonic RISE anastomosis (intervention) in improving postoperative stool formation time (primary outcome) in patients with right hemicolectomy for colorectal cancer compared with traditional side-to-side

anastomosis.

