## **III. RESEARCH DESIGN**

### **1. Research on the overall design**

This prospective, single-blind, double-arm, multicenter, randomized controlled clinical trial with superiority design aims to compare postoperative intestinal function recovery between complete laparoscopic/robot-assisted right hemicolectomy combined with RISE anastomosis and traditional side-to-side anastomosis in patients with right-sided colon cancer. Eligible participants will be randomly assigned into RISE anastomosis and conventional anastomosis groups through zonal randomization, with evaluation of key outcomes including postoperative bowel function recovery (primary endpoint), complications, nutritional metabolism, quality of life, and oncological prognosis. Patients must provide informed consent prior to surgery, and all procedures are performed by senior physicians with extensive experience at each

center to ensure standardized protocols.

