Figure 2 Schematic of RISE anastomosis steps. A-B: Identify and mark the transection sites on the transverse colon stump and terminal ileum. C-D: Evert the terminal ileum to mimic the anatomical structure of the ileocecal valve. E-F: Place fixation sutures at the transverse colon opening. G-H: Complete the RISE anastomosis of the terminal ileum with colon.

b. Conventional lateral side anastomosis group (control group)

After inserting the same cannula, ligating blood vessels, and making a 10 cm distal transection at the transverse colon mass along with a 15 cm proximal transection at the ileocecal valve, the specimen was extracted through a small midline incision. A linear stapler was used in vitro for the side-to-side ileocolonic anastomosis, followed by closure of the common intestinal incision with a second stapler. The anastomotic site was reinforced with 3-0 catgut sutures using reverse-staple technique.

(2) Intraoperative index recording:

- Total operation time (min);
- Surgical duration of anastomosis (min);
- Blood loss during operation (mL);
- Blood transfusion volume (mL);
- 

(3) Immediate postoperative monitoring:

- Blood pressure, heart rate, respiration and body temperature at 24h, 48h and 72h after surgery;
- Daily postoperative physical examination (abdominal signs, resumption of bowel sounds);
- Bristol stool score (recorded daily for 7 consecutive days);

(4) Laboratory test:

Blood routine and blood biochemistry (monitoring inflammatory indicators and metabolic status) at 24h and 72h after surgery;

(5) Postoperative complication records (according to Clavien-Dindo grading system):

Table 1. Clavien-Dindo grading system for surgical complications

I	
 
① Abnormal conditions that do not require medication or surgery, endoscopy and radiation therapy.
 
② Antispasmodic, antipyretic, analgesic, diuretic, electrolyte and other drug therapy and physical therapy.
 
③ Open infected wounds at the bedside
 

II	
 
① Complications requiring the use of medications other than those described above for treatment of grade I complications.
 
② Blood transfusion, total parenteral nutrition
 

III	Complications requiring surgery, endoscopy or radiation therapy
IIIa	No general anesthesia is required
IIIb	Need general anesthesia

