## **5. End-point indicators**

Key endpoint indicator: Time to first stool formation post-surgery (Bristol Stool Score <4): The Bristol Stool Scale categorizes stool into seven grades. As stool shape correlates with retention time in the colon, this score helps assess both intestinal transit time and anastomotic function. Scoring criteria: >5 indicates diarrhea, 6 represents mild diarrhea, and 7 signifies severe diarrhea. (Detailed scoring guidelines are provided in the appendix)

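### The primary endpoint is a time observed only to day 7, but neither the planned tests nor the sample-size basis is aligned with it

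*Protocol*

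**What the plan says.** All references are to the protocol.

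- **Endpoint.** The main objective (II.1) speaks of "improving postoperative stool formation time (primary outcome", and III.5 defines the key endpoint as "Time to first stool formation post-surgery", with the event being a Bristol score below 4. The design summary (III.1) uses a looser label, "postoperative bowel function recovery (primary endpoint".
- **Measurement.** Under Treatment in III.4, immediate postoperative monitoring includes "Bristol stool score (recorded daily for 7 consecutive days". The research process table ticks the Bristol score at 24, 48 and 72 hours and again from 1 month. It has no column for days 4 to 7.
- **Tests.** III.6 gives chi-square for categorical data. For the rest: "Quantitative data, validated by S-W method testing for normal distribution, are expressed as" mean and SD, and compared by t-test. It names no rank or survival method.
- **Missing data.** III.6 keeps lost cases in the intention-to-treat analysis and adds that "multiple interpolation was used to fill in the missing data".
- **Sample size.** III.3 states: "The postoperative stool formation time served as the primary endpoint for sample size calculation". The figures that follow are proportions: "the stool formation rate was approximately 65% in the RISE group and 33.3% in the control group on day 2 postoperatively". They lead to 85 per group, then 94 per group and 188 in all.
- **Left to the SAP.** V.7 assigns only the handling of centre effects to the statistical analysis plan.

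**The concern.** A time read once a day over 7 days has two features that the tests in III.6 do not accommodate.

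1. It is right-censored. A patient observed to day 7 without the event has a time known only to exceed 7 days. This is plausible on the protocol's own terms: the event needs a score below 4, while the annotations describe grade 4 as the standard normal form. A t-test needs a number for that patient, and III.6 gives none. The imputation sentence does not help, because it concerns lost and missing cases. Imputing an outcome that was observed not to occur would be wrong.
2. It takes only a handful of whole-day values, so the Shapiro-Wilk condition attached to the t-test would hardly ever be met.

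Chi-square suits the day-2 proportion used in III.3, but that is not the endpoint. Endpoint, tests and sample-size basis therefore point in different directions. At stake are the size and meaning of the primary estimate, and whether the analysis is fixed before results are seen.

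**Working it through.** **Inputs.** Day-2 rates 65% and 33.3%, two-sided alpha 0.05, 85 per group (all III.3); daily recording to day 7 (III.4).

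**The plan's own figure.** For two proportions, n = [z(α/2)·√(2p̄q̄) + z(β)·√(p₁q₁ + p₂q₂)]² / (p₁ − p₂)², with p̄ = 0.4915 and p₁ − p₂ = 0.317. This gives 38 per group at 80% power, 51 at 90%, 62 at 95% and 87 at 99%. With 85 per group the power is 98.9%. The visible text states no power and the software output is a figure that is not shown, so whether 85 reproduces cannot be decided and is not held against the plan. The rest follows: 85 × 1.10 = 93.5, rounded to 94, and 2 × 94 = 188. The calculation is one for proportions; no time enters it.

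**Assumptions for the time.** The protocol gives no distribution. Assume that the day-2 rates are cumulative (III.3 does not say so) and that S(t) = exp[−(t/s)^k] in each arm, with a common shape k and s set so that 65% and 33.3% have the event by day 2. Times are rounded up to whole days.

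**Worked case, k = 1.** Then S(t) = (1 − p)^(t/2).
- Day 7: control 0.667^3.5 = 0.242; RISE 0.35^3.5 = 0.025.
- The mean time restricted to 7 days is the sum of S(0) to S(6).
- Control: 1 + 0.817 + 0.667 + 0.545 + 0.445 + 0.363 + 0.297 = 4.134.
- RISE: 1 + 0.592 + 0.350 + 0.207 + 0.122 + 0.072 + 0.043 = 2.386.
- Difference: 1.75 days.
- Expected events: 85 × (2 − 0.242 − 0.025) = 147.

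| Shape k | Control, no event by day 7 | RISE, no event by day 7 | Events of 170 | Mean difference, non-events counted as 7 (days) | Shift per extra day assigned to non-events (days) |
|---|---|---|---|---|---|
| 0.7 | 37.8% | 8.0% | 131 | 1.89 | 0.378 − 0.080 = 0.298 |
| 1 | 24.2% | 2.5% | 147 | 1.75 | 0.242 − 0.025 = 0.217 |
| 1.5 | 7.1% | 0.1% | 164 | 1.39 | 0.071 − 0.001 = 0.070 |
| 2 | 0.7% | 0.0% | 169 | 1.05 | 0.007 − 0.000 = 0.007 |

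The last column shows why the rule matters. The value given to a non-event is arbitrary, and each day added to it moves the estimated difference by the gap between arms in the proportion without the event.

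**Normality condition.** In 4,000 simulated trials per shape (16,000 in all, 85 per arm, whole-day times), Shapiro-Wilk rejected normality in both arms every time.

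**Power at the planned effect, common shape.** Day-2 chi-square 98.7% to 99.0%; t-test with non-events set to 7, and log-rank, at least 99.95%.

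**Events for a log-rank test.** Under proportional hazards, HR = ln(0.35)/ln(0.667) = 2.59. Schoenfeld: 4(1.960 + 0.842)²/(ln 2.59)² = 34.6, so 35 events for 80% power; with 1.282 in place of 0.842 it is 46.3, so 47 for 90%. Under the common-shape assumption 131 to 169 are expected by day 7.

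**The case against.** **Much of this belongs in a SAP.** III.6 is a general paragraph, it ties no test to the primary endpoint, and V.7 shows that a SAP is intended. A fallback for non-normal data and a day-7 rule are often put there. This stands in part, and silence alone would not be a finding. But III.6 is not silent: it fixes a menu of tests, none of which suits the endpoint. The mismatch between III.3 and III.5 also lies within the protocol itself.

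**A t-test is robust at this size.** True. With 85 per arm, non-normality alone does little harm; in a check with non-events set to 7, rejection under the null was 5.2% to 5.6%. The normality result also depends on whole-day rounding. With continuous, uncensored control times of shape 2, rejection falls to about 69%, and with a clipped normal distribution (SD 1.5 days) to about 20%. The weight of the point therefore lies on censoring and on a test condition the data will probably fail, not on non-normality as such. If every patient is observed to day 7, setting non-events to 7 makes the t-test compare restricted means, which is a sensible quantity; the protocol does not say so.

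**The remedy is not always more powerful.** Also true. With true day-2 rates of 50% and 33.3% and a common shape, log-rank (84% to 92%) and the t-test (79% to 90%) beat the day-2 chi-square (about 61%). With shape 1 for RISE and 1.5 for control, the order reverses: chi-square 60%, t-test 43%, log-rank 21%.

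**Readings that go too far.**
- A reader might infer two competing primary endpoints and an inflated type I error. Taking whichever of chi-square and t-test is significant would give 7.4% to 7.8%. But II.1, III.3 and III.5 all name the time, the day-2 rate is only a planning input, and the label in III.1 is a loose summary. The text does not license that choice.
- A reader might infer that the effect could be more than halved. That needs non-events to be dropped, which the protocol does not propose and its intention-to-treat sentence fits poorly. Even then only shape 0.7 loses more than half (0.71 of 1.89 days, 38% retained); shapes 1, 1.5 and 2 retain 54%, 82% and 97%.

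**Conclusion.** The point holds as a misalignment that should be fixed. The endpoint is a whole-day time, right-censored at day 7; neither test named in III.6 suits it; and III.3 claims the time as its basis while calculating from day-2 proportions.

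The consequence depends on how many patients have no event by day 7, and the protocol's figures cannot settle that. With cumulative day-2 rates and a common Weibull shape from 0.7 to 2, it is about 38% to 0.7% of controls and 8% to 0% of RISE patients. The effect of their handling on the estimate then runs from large to negligible.

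A reader might infer that the trial is underpowered. The documents do not support this: under the same assumptions every candidate test has about 98% power or more at the planned effect. At smaller effects, which test is stronger depends on the curve shapes, so no general power advantage is claimed for the log-rank test. The reason to prefer it is that it uses the endpoint as defined and keeps patients with no event.

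**What to change.** In III.6, name one primary analysis in all randomised patients:

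- Kaplan-Meier curves and a two-sided log-rank test, with the method for ties stated, censoring at day 7 patients who have had no formed stool.
- The 7-day restricted mean difference as the single effect estimate. It does not need proportional hazards.
- A statement that imputation does not apply to patients observed to day 7 without the event, and that the 1-month Bristol score does not supply an event time.
- The day-2 proportion by chi-square as a supporting analysis.

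In III.3, say that the day-2 proportion is the planning basis. Use one name for the primary endpoint in II.1, III.1, III.3 and III.5. As a secondary item, reconcile the Bristol row of the research process table with the daily 7-day recording in III.4, by a column or footnote for days 4 to 7.

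The cost is a few sentences, a table edit and slightly more analysis work. No extra patients are needed.

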**Exit criteria:**

- a. Subjective withdrawal: the patient explicitly refuses to continue to participate in the study or adopts the anastomosis method of reconstructing the ileocecal valve.
- b. Withdrawal by the investigator:
  - During or after the operation, complicated conditions (such as severe abdominal adhesion, more difficult than expected) are found, which make it impossible to complete the operation according to the established plan.
  - The patient's postoperative condition changes (such as severe complications, infection, etc.) are not suitable for continued participation in the study after evaluation by the investigator.
- c. Missing follow-up: the patient is unable to complete the follow-up (e.g., lost

contact, refusal to further examination).

d. Protocol deviation: the subject did not receive the intervention or follow-up as required by the study protocol, affecting the validity of the data.

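### One multiple-imputation rule covers all missing data of lost cases and does not set apart the time-to-event endpoints, where loss calls for censoring

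*Protocol*

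**What the plan says.** The missing-data rule stands at the end of protocol section III.6 (Data management and statistical analysis): "The lost cases were included in the intention-to-treat (ITT) analysis, and multiple interpolation was used to fill in the missing data". I take interpolation to mean imputation. The rule names no endpoint, no reason for missingness and no time limit.

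The same section gives the tests. Categorical data go to chi-square tests, and normally distributed quantitative data are "evaluated using t-tests". It names no survival method and no censoring rule.

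The endpoints that the rule meets include three times to an event:

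- **Primary (III.5, End-point indicators):** "Time to first stool formation post-surgery (Bristol Stool Score <4". The source data are described under Treatment in III.4: "Bristol stool score (recorded daily for 7 consecutive days".
- **Survival objective (II.2, Secondary purposes):** "To explore the long-term effects of RISE anastomosis on overall survival (OS) and progression-free survival (PFS".
- **Survival endpoint (III.5, secondary endpoint d):** "The total survival and tumor-free survival of patients after surgery", with recurrence and metastasis assessed at one year. The objective says progression-free and the endpoint says tumor-free; I treat them here as one endpoint beside overall survival.

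The exit criteria in III.2 describe who counts as lost: "Missing follow-up: the patient is unable to complete the follow-up". The examples given are lost contact and refusal of further examination.

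**The concern.** Loss to follow-up leaves different things behind for different outcomes. For a laboratory value at a missed visit, the value is simply unknown, and imputing it from earlier visits and covariates is reasonable. For a time to event, the patient has already supplied part of the answer: no event had occurred by the last contact. The standard way to use that part is to keep the patient in the risk set until last contact and censor there.

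The protocol does not separate the two cases. It prescribes filling in, and the only tests beside that prescription need a complete value for every patient: a number for the t-test, a category for the chi-square test. An analyst who followed the section as written would fill in a stool-formation day, or a survival time or status, for each lost patient. Nothing in the text requires that value to agree with the event-free follow-up already on record. At stake is the use of real follow-up data in the primary endpoint and both survival endpoints.

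**Working it through.** The point rests on reading the rule against the endpoints. Arithmetic enters only for the number of patients affected.

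**Step 1. How many patients the rule would touch.** Inputs are from III.3 (Sample size): 85 per group before dropout, 10% dropout, and site quotas of 108 and four times 20.

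- Inflated size per group: 85 × 1.10 = 93.5, rounded up to 94, as the protocol states.
- Total: 2 × 94 = 188, which agrees with 108 + 4 × 20 = 188.
- Allowance for loss: 188 − 2 × 85 = 18 patients, or 18/188 = 9.6%.

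The 10% is not tied to a time point, so these 18 may be lost at any time up to one year.

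**Step 2. What is known about a lost patient.** Let T be the time to the event and c the time of last contact without it.

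- Time to first formed stool, lost before day 7: T > c days is known.
- Overall survival, last seen alive at, say, the 6-month visit: T > 6 months is known.
- Progression-free or tumor-free survival, last assessed free of recurrence at that visit: T > 6 months is known.
- Albumin, total protein, vitamin B12, bile acid, body composition or quality of life at a missed visit: the record holds no such bound on the value.

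The first three are partly observed. The last group is missing in the ordinary sense.

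**Step 3. What each handling does with T > c.**

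- Censoring at c: the patient contributes the probability of being event-free at c, S(c), and stays in the risk set until then. All observed follow-up is used.
- Filling in T without a constraint: a drawn value falls at or before c with probability 1 − S(c) under the distribution used, and every such draw contradicts the patient's own record.
- Filling in T subject to T > c: there is no contradiction. This is a legitimate form of multiple imputation, but the protocol does not ask for it.

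**Step 4. Where it bears most.** The primary endpoint is read from daily records in the first 7 postoperative days, whereas follow-up visits run at 1, 3 and 6 months and 1 year. Most loss can be expected after the first week, so few of the 18 should lack the primary outcome. The survival outcomes depend on contact up to one year and are exposed to all of the loss.

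**Step 5. What cannot be computed.** The protocol gives no one-year mortality, no recurrence rate, no timing of loss and no imputation model. I therefore give no figure for the shift in any treatment difference.

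**The case against.** The strongest reply is that the sentence is a one-line principle and that variable-level imputation rules belong in the SAP, which is not shown. That stands for the choice of model and covariates. It does not fully answer the point, because the protocol is not silent. It states a positive rule, and that rule does not suit three named endpoints. The protocol's reference to the SAP, in V.7, concerns center effects; section III.6 does not refer missing data to it.

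A second reply is that multiple imputation can respect a known lower bound. That is true, and it is why the problem is a badly fixed rule rather than a certain error.

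Three stronger readings are tempting, and the protocol does not support them.

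- A reader might infer that values after death would be invented. The rule is tied to lost cases, and the examples under the exit criteria do not include death. The text fails to exclude such values, but it does not say that they are filled in.
- A reader might infer that a day without a bowel movement would be imputed. A patient under daily observation is not a lost case. Nor is one followed through day 7 without a formed stool, although that patient too needs a censoring rule.
- A reader might infer that the bias favours the better arm. Imputation within arm under missing at random does not do so in general, and censoring makes a similar assumption about patients lost. If arm is left out of the imputation model, the distortion can run toward no difference. The case for censoring is that it uses the observed follow-up, not that it removes the assumption.

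**Conclusion.** The point holds in a limited form. Section III.6 fixes one imputation rule for all outcomes of lost cases. Read literally, beside t-tests and chi-square tests alone, it replaces known event-free follow-up with a filled-in value for time to first formed stool, overall survival, and progression-free or tumor-free survival. Censoring at last contact is the better rule and costs nothing.

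The reach is about 18 of 188 patients if loss runs as planned. The effect on the primary comparison is probably small, and the rule alone is unlikely to overturn the primary result. It matters more for the one-year survival outcomes. Neither a direction nor a size of bias can be claimed from the document.

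The conclusion assumes that the rule is applied as written and that no unseen SAP text narrows it. If the SAP already censors these endpoints, only the protocol wording needs to be aligned with it.

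**What to change.** Replace the follow-up sentence in III.6 with two that separate the outcome types. For example:

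*Visit-based measurements (albumin, total protein, vitamin B12, bile acid, body composition, quality of life) that are missing in patients alive at that visit will be multiply imputed. Time to first formed stool, overall survival and progression-free or tumor-free survival will be analysed with survival methods, with patients who have not had the event censored at the last observed day or last contact.*

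The words on being alive at the visit settle the status of values after death, which the current text leaves open.

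Optionally, add one sensitivity analysis of the primary endpoint that counts patients lost before a formed stool as not formed by day 7.

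The cost is about two sentences in the protocol, repeated in the SAP. The change needs no new data and leaves the sample size and visit schedule as they are. It should be made before the data are analysed.
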